9.3 Analysis Sets

Population	Definition
Intent-to-Treat Analysis Set	All subjects randomized.
Safety Analysis Set	All subjects randomized who receive at least one dose of study medication.
PK Analysis Set	All subjects with at least 1 ENTO plasma concentration
Biomarker Analysis Set	All subjects with at least 1 biomarker assessment result

9.4 Statistical Analyses

Detailed methodology for summary and statistical analyses of the data collected in this study will be documented in a Statistical Analysis Plan (SAP). Described below is a summary of the planned statistical analyses of the primary and key secondary endpoints.

9.4.1 General Considerations

Summary statistics and listings will be used to analyze the study data. Continuous variables will be summarized by means, standard deviations, medians, interquartile ranges, minimal and maximal values. Categorical variables will be summarized by number and percentage. Any statistical testing will be conducted at the alpha = 0.05 level (2-sided).

Unless otherwise specified, data summaries and analyses described below will be reported by treatment group.

9.4.2 Primary Endpoint

Measurable Residual Disease Negative Complete Response

The primary efficacy endpoint is the proportion of subjects who achieve CR without MRD (MRD negative [$<0.01\%$] CR rate) Post-Chemotherapy Cycle 2 as defined by the absence of *NPM1*-m alleles in bone marrow aspirate based on a molecular assay (eg, next generation sequencing) in a central reference laboratory designated by the Sponsor.

9.4.2.1 Statement of Estimand

The **population for the trial** is defined through appropriate inclusion/exclusion criteria to reflect the targeted patient population for approval, adults with previously untreated *NPM1*-m AML who are candidates for intensive induction/consolidation chemotherapy. The analysis population is based on the Intent-to-treat Analysis set and includes subjects who have been randomized.

The **treatments** of interest are ENTO or placebo in combination with intensive induction and consolidation chemotherapy.

The **variable** of interest is the MRD negative CR rate post-Chemotherapy Cycle 2.

The ability to evaluate treatment effect using the variable may be impacted by **intercurrent events**. Death, use of additional leukemic treatments, and premature discontinuation of study drug may all impact the interpretation of treatment effect. Given that death equates to a poor outcome, a composite strategy will be implemented including all available data through the evaluation of response post-Chemotherapy Cycle 2; subjects who die before the end of Chemotherapy Cycle 2 will be considered as not having achieved MRD negative CR.

The **population level summary measure** is the risk difference (difference in the proportion of subjects with MRD negative CR Post-Chemotherapy Cycle 2).

CONFIDENTIAL

Protocol KB-ENTO-3001 v4.0

(Amendment 3.0)

9.4.2.2 Primary Endpoint Analysis

The primary evaluation of the primary analysis endpoint will be conducted utilizing the estimand as described in [Section 9.4.2.1](#). Subjects with a missing evaluation of MRD post-Chemotherapy Cycle 2 will be imputed as failures for the analysis. Additional information on the handling of missing data, planned sensitivity measures, and supportive analyses will be detailed in the SAP.

Risk difference will be estimated using stratum-adjusted Mantel-Haenszel proportions, and 95% confidence intervals around the treatment difference will be calculated. The differences are weighted by the harmonic mean of the sample size in each treatment group per stratum (age < 60 vs ≥ 60 years; daunorubicin vs idarubicin anthracycline). If n_{1h} and n_{2h} are the sample sizes of the two treatment groups for a given comparison, say treatment groups 1 and 2, in any given stratum, called stratum h, then the weight in stratum h is given by,

$$w_h = \frac{n_{1h} n_{2h}}{n_{1h} + n_{2h}}$$

Let $d_h = p_{1h} - p_{2h}$ be the difference in the proportion of subjects with MRD negative CR in treatment group 1 and treatment group 2 in stratum h. The stratum-adjusted Mantel-Haenszel proportion is given by,

$$d = \frac{\sum_h w_h d_h}{\sum_h w_h}$$

The continuity corrected variance is given by,

$$\text{var} = \frac{\sum_h w_h^2 \left(\frac{p_{1h}^* (1 - p_{1h}^*)}{n_{1h} - 1} + \frac{p_{2h}^* (1 - p_{2h}^*)}{n_{2h} - 1} \right)}{\left(\sum_h w_h \right)^2}$$

where $p_{1h}^* = \frac{m_{1h} + 0.5}{n_{1h} + 1}$, $p_{2h}^* = \frac{m_{2h} + 0.5}{n_{2h} + 1}$, m_{1h} and m_{2h} are the number of subjects with MRD negative CR in treatment groups 1 and 2, respectively.

9.4.3 Secondary Endpoint(s)

The secondary endpoint variables and their population level summary measures will be described in each of the following sections. The evaluation of the population for the trial, treatments of interest, and the possible intercurrent events are as described in [Section 9.4.2.1](#). All secondary endpoints will include death as part of definition of the variable. Intercurrent events of additional leukemic therapy and premature study treatment discontinuation will be ignored for the primary evaluation of these endpoints. Additional information on the handling of missing data and sensitivity analyses will be detailed in the SAP.

CONFIDENTIAL

Protocol KB-ENTO-3001 v4.0

(Amendment 3.0)

Event-free survival

Event-free survival (EFS) is defined as time from randomization to the earliest of induction treatment failure (ITF), relapse for those who achieve CR, or death from any cause. ITF is failure to achieve morphological CR after completion of the last cycle of induction chemotherapy (no later than Day 42 of the last cycle of induction). Subjects who experience ITF will be treated as events at Day 1.

Subjects who do not experience an event (ITF, relapse from CR, or death) will be censored at their last study evaluation at which they were relapse free. Event-free survival will be estimated using the method of Kaplan-Meier (K-M) and summarized by treatment group. Differences between the treatment groups will be assessed with the log rank test stratified by age (<60 vs \geq 60 years) and choice of anthracycline in induction (daunorubicin vs idarubicin). The population level summary measure will be the adjusted hazard ratio as calculated from a Cox proportional hazards model with effects for treatment, age, and choice of anthracycline in induction.

Relapse free survival

For subjects who achieve CR, relapse free survival (RFS) is defined as the time from CR to morphologic relapse as assessed by the study site investigator or death from any cause, whichever comes first. Subjects who do not experience a relapse or death will be censored at the last study evaluation at which they were relapse free. RFS will be estimated using the K-M method and summarized by treatment group. The population level summary measure will be the adjusted hazard ratio as calculated from a Cox proportional hazards model with effects for treatment, age, and choice of anthracycline in induction.

Overall survival

Overall survival is defined as the time from randomization to death from any cause. Subjects who are alive at last contact will be censored at their date of last contact. Overall survival will be estimated using the K-M method and summarized by treatment group. Differences between the treatment groups will be assessed with the log rank test stratified by age (< 60 vs \geq 60 years) and choice of anthracycline in induction (daunorubicin vs idarubicin). The population level summary measure will be the adjusted hazard ratio as calculated from a Cox proportional hazards model with effects for treatment, age, and choice of anthracycline in induction.

Categorical secondary endpoints will be analyzed similarly to the primary efficacy endpoint, and other time-to-event secondary endpoints will be analyzed similarly to EFS. To avoid inflation of Type I error for the secondary endpoints, statistical comparisons will be made at the time of the confirmatory analysis using a hierarchical approach with EFS tested first followed by RFS, and then overall survival. Details of the hierarchical analysis will be provided in the SAP.

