3.0 Objectives and Endpoints

Objectives	Endpoints
Primary	

 To evaluate the efficacy of ENTO compared to placebo when added to chemotherapy in previously untreated NPM1-m AML, as defined by the rate of molecularly defined measurable residual disease (MRD). 	
 MRD negative CR rates after completion of 2 cycles of chemotherapy plus either ENTO or placebo. 
Note: MRD negative CR requires CR as defined by ELN 2017 criteria (with minor modification for neutrophil and platelet count thresholds as defined by the International Working Group [IWG]) as assessed by study site investigators, and MRD negativity (<0.01%) in bone marrow as measured by a molecular NPM1-m assay (eg, next generation sequencing) in a central laboratory upon recovery of peripheral blood counts following completion of 2 cycles of chemotherapy (ie, no later than Day 42 of Cycle 2).

Secondary	

 To evaluate the efficacy of ENTO compared to placebo when added to chemotherapy in previously untreated NPM1-m AML, as defined by relapse-free, event-free, and overall survival. 	
 Event-free survival, defined as the time from randomization to the earliest occurrence of induction treatment failure, relapse from CR, or death from any cause. 
Note: Induction treatment failure is failure to achieve morphological CR after completion of the last cycle of induction chemotherapy (no later than Day 42 of the last cycle of induction).
 
 Relapse-free survival, defined as the time from CR until relapse or death from any cause as assessed by study site investigators. Overall survival defined as the time from randomization until death from any cause.

 To evaluate the efficacy of ENTO compared to placebo when added to chemotherapy in previously untreated NPM1-m as defined by CR rate. 	
 CR rates after 2 cycles of chemotherapy, as defined by ELN 2017 criteria (with minor modification for neutrophil and platelet count thresholds as defined by the IWG) as assessed by study site investigators.

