7.0 Discontinuation of Study Treatment/Participation

7.1 Discontinuation of Study Treatment

Subjects may discontinue study medication at any time at his/her own request or may be discontinued at the discretion of the investigator for safety, behavioral, or compliance reasons.

Subjects must discontinue study medication for the following reasons:

- Recurrence of leukemia after a response
- Failure to achieve (or maintain) CR, CRh or CRI post-Chemotherapy Cycle 2
- Death
- Withdrawal of consent
- An AE or intercurrent illness that precludes further administration of protocol therapy or participation in the study
- Need for, or use of a prohibited concomitant medication
- Hematopoietic stem cell transplantation
- Pregnancy

If study treatment is permanently discontinued for any reasons, subjects shall remain in the study for long-term follow-up. See [Table 7](#) for assessments required for the End-of-Treatment evaluation and long-term follow-up.

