- Persistent bone marrow blast percentage $> 70\%$ over ≥ 3 months without at least a 100% improvement in ANC to an absolute level $> 0.5 \times 10^9/L$ ($500/\mu L$) and/or platelet count to $> 50 \times 10^9/L$ ($50,000/\mu L$) without transfusion, or
- $> 50\%$ increase in circulating blasts to $> 25 \times 10^9/L$ ($> 25,000/\mu L$) in the absence of Differentiation Syndrome,**** or
- New extramedullary disease

**** Certain targeted therapies, for example, those inhibiting mutant IDH proteins, other kinase or targets may cause a transient increase in the percentage of bone marrow blasts accompanied by an increase in circulating blasts (differentiation syndrome). In the setting of therapy with such compounds, an increase in blasts may not necessarily indicate progressive disease. Such instances should be discussed with the study medical monitor on a case-by-case basis.

Recurrence

Recurrence for subjects with prior MRD-CR, morphological CR, CRh, CRi, or MLFS is defined as:

Morphologic relapse as defined by the reappearance of circulating blasts or $\geq 5\%$ blasts in the bone marrow not attributable to any other cause.

Note: In the setting of recent treatment, if there are no circulating blasts and the bone marrow contains 5 to 20% blasts, a bone marrow aspirate/biopsy should be repeated within 1 week to distinguish relapse from bone marrow regeneration.

Reappearance of cytologically or biopsy documented extramedullary disease, including new CNS disease or other new sites of extramedullary involvement.

Note: The reappearance of a cytogenetic or molecular abnormality would be considered a cytogenetic or molecular relapse. In the absence of morphologic relapse, this would not be considered a recurrence.

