- Morphologic relapse as defined by the reappearance of circulating blasts or $\geq 5\%$ blasts in the bone marrow not attributable to any other cause. *Note: In the setting of recent treatment, if there are no circulating blasts and the bone marrow contains 5 to 20% blasts, a bone marrow aspirate/biopsy should be repeated within 1 week to distinguish relapse from bone marrow regeneration.*
- Reappearance of cytologically or biopsy documented extramedullary disease, including new CNS disease or other new sites of extramedullary involvement. *Note: The reappearance of a cytogenetic or molecular abnormality would be considered a cytogenetic or molecular relapse. In the absence of morphologic relapse, this would not be considered a recurrence.*

Evaluation of response is recorded on the Response Assessment eCRF, and documentation of recurrence (relapse) is recorded on the Relapse Assessment eCRF.

Adverse Event

An AE is defined as any untoward medical occurrence in a clinical study subject, temporally associated with the use of study treatment, whether or not considered related to the study treatment.

Treatment-emergent Adverse Event (TEAE)

A TEAE is any adverse event beginning or worsening from C1D1 through 30 days following study treatment completion.

Treatment-emergent Laboratory Toxicity (TELT)

A TELT is a laboratory abnormality as defined in the National Cancer Institute - Common Toxicity Criteria for Adverse Events (NCI-CTCAE) v5.0 (NCI 2017, which occurs on or after the start of study treatment and up to 30 days following discontinuation of all study treatment and is at least 1 grade shift from the baseline value. TELTs are determined programmatically from laboratory assessments recorded in the relevant CRF pages.

Concomitant Medications

Concomitant medications are those medications taken on or after the initiation of study treatment. This includes medications started prior to the initiation of ENTO/placebo and continued after the initiation of ENTO/placebo. These medications will be recorded in the Prior and Concomitant Medications page of the CRF.

Prior Medications

Prior medications are those medications taken and discontinued prior to the initiation of study treatment. These medications will be recorded in the Prior and Concomitant Medications page of the CRF.

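### RFS has two event definitions: the endpoint tables end it at relapse, Protocol 9.4.3 ends it at morphologic relapse, and an isolated extramedullary or CNS recurrence falls between them

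*Protocol*

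**What the plan says.** **Endpoint tables.** Protocol 3.0 has "Relapse-free survival, defined as the time from CR until relapse or death from any cause as assessed by study site investigators". The Synopsis and the table in SAP section 3 define RFS in the same terms. None of the three qualifies the word relapse.

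**Analysis text.** Protocol 9.4.3 narrows the event: "relapse free survival (RFS) is defined as the time from CR to morphologic relapse as assessed by the study site investigator", or death if that comes first. The censoring sentence in the same paragraph drops the qualifier: "Subjects who do not experience a relapse or death will be censored at the last study evaluation at which they were relapse free".

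**Response criteria.** Protocol Appendix 4 and SAP 4.4.4 define recurrence by two routes. The first is "Morphologic relapse as defined by the reappearance of circulating blasts or" at least 5% marrow blasts with no other explanation. The second is "Reappearance of cytologically or biopsy documented extramedullary disease, including new CNS disease or other new sites of extramedullary involvement". The SAP makes clear that either is enough. On molecular or cytogenetic reappearance, Appendix 4 adds: "In the absence of morphologic relapse, this would not be considered a recurrence".

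**Related rules.** Among the reasons to stop study medication, Protocol 7.1 lists "Recurrence of leukemia after a response". EFS in 9.4.3 counts relapse, again unqualified. RFS is tested second in the hierarchy, after EFS and before OS.

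**The concern.** An event rule should place every subject in exactly one of two states at the analysis cut-off: event on a known date, or censored on a known date. Two programmers working from this plan could place the same subject differently. One following the endpoint tables would count an isolated extramedullary or CNS recurrence on its date. One following the 9.4.3 definition would leave the subject at risk.

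The narrow reading also conflicts with what RFS measures. Under Appendix 4, CR itself requires that no extramedullary disease be present. A subject with documented extramedullary recurrence no longer meets the criteria for the remission whose length is being measured, yet would still be event-free. Because 9.4.3 disregards additional leukemic therapy for the secondary endpoints, starting salvage would not end the RFS interval either. If salvage cleared the site, the failure might never enter the analysis.

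**Working it through.** The plan states no sample size, event count or power for RFS, so there is no figure to reproduce. The check is on the text, using one test case: a subject in CR who develops biopsy-proven extramedullary or CNS leukemia, with no circulating blasts and marrow blasts below 5%.

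| Rule | Term used | Does the test case count? |
|---|---|---|
| Recurrence, Appendix 4 and SAP 4.4.4 | recurrence, either route | Yes, second route |
| Study-medication rule, Protocol 7.1 | recurrence | Yes, if still on study medication |
| RFS, Synopsis, Protocol 3.0, SAP section 3 | relapse | Yes, if relapse means recurrence |
| EFS, Protocol 9.4.3 | relapse | Probably, on the same condition |
| RFS event, Protocol 9.4.3 | morphologic relapse | No, on the Appendix 4 meaning |
| RFS censoring, Protocol 9.4.3 | relapse | Not clearly eligible for censoring |

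**The link between relapse and recurrence.** Appendix 4 defines recurrence, not relapse. The bridge is in SAP 4.4.4, which treats the two words as synonyms when it names the Relapse Assessment eCRF as the place where they are recorded. The rows marked as conditional depend on that link.

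**What follows for RFS.** Three treatments of the test case can be defended:

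1. Endpoint tables: event on the date of the extramedullary recurrence.
2. 9.4.3, with morphologic carried into the censoring sentence: no event yet. The subject stays at risk until blood or marrow relapse, death or the last evaluation.
3. 9.4.3 exactly as written: not an event by the definition, and not among those without a relapse whom the censoring sentence covers. Censoring at the last relapse-free evaluation anyway would remove the subject just before a treatment failure.

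**Illustration of size (assumed inputs).** The share of recurrences that are isolated extramedullary or CNS is not in the documents. If it were 2% to 10%, then among an assumed 40 recurrences in CR subjects the number affected would be 0.02 × 40 = 0.8 to 0.10 × 40 = 4, or about 1 to 4.

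For a rough view of power, take the EFS target (124 events, hazard ratio 0.6, two-sided 0.05) as a stand-in for RFS. The Schoenfeld formula needs 121 events for 80% power and the Freedman formula 126, so the planned 124 is a reasonable base. Schoenfeld power is Φ(√(D/4) × |ln 0.6| − 1.96):

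| Events lost (assumed) | D | Power |
|---|---|---|
| 0% | 124 | 81% |
| 2% | 122 | 80% |
| 5% | 118 | 79% |
| 10% | 112 | 77% |

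Even a 10% loss moves power by about 4 points. The weakness is in the definition, not mainly in power.

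**The case against.** The strongest reply is that morphologic was meant only to rule out molecular relapse. The protocol does use the word that way elsewhere: MRD is followed until morphologic relapse and is to be correlated with it. The Appendix 4 note draws the same contrast, and if morphologic strictly meant blood or marrow blasts, that note would sit awkwardly for a subject with molecular reappearance plus biopsy-proven extramedullary disease. Protocol 9.4 also calls itself a summary that defers detail to the SAP. The three endpoint tables, the censoring sentence and the SAP's equation of recurrence with relapse all favour counting the extramedullary event.

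Much of this stands, and it limits the finding. A reader might infer that RFS is settled to omit extramedullary recurrences, that it therefore overstates remission duration, and that EFS and RFS must disagree. The documents do not support that. The exclusion rests on one sentence, and counting the event under EFS is an inference through SAP 4.4.4, a link that would equally bring it into RFS as the tables define it. The comparison with 7.1 is also limited, because study medication ends no later than the end of consolidation while RFS follow-up continues. Disregarding salvage therapy is a stated choice, not an oversight.

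The reply does not remove the conflict. Appendix 4 already keeps molecular or cytogenetic reappearance alone out of recurrence, so the qualifier is not needed for that purpose, and its defined meaning also takes out extramedullary disease. The SAP contains no RFS derivation that settles which wording governs.

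**Conclusion.** The plan holds two RFS event definitions that classify an isolated extramedullary or CNS recurrence differently, and the 9.4.3 paragraph is not consistent within itself. Followed literally, 9.4.3 would misclassify such subjects on an endpoint ranked second in the testing hierarchy. This rests on Appendix 4's meaning of morphologic relapse; the probable disagreement with EFS rests also on the SAP treating recurrence and relapse as one.

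The size is unknown. The 2% to 10% share and the 40 recurrences are assumptions used for scale, the power figures borrow the EFS target, and nothing indicates which arm would be favoured. No reported result is affected: 15 subjects were randomized before termination, and SAP 6.4 rules out analysis of the protocol-defined primary and secondary efficacy endpoints. The point matters for the protocol as designed, and for any later derivation of RFS or reuse of these definitions.

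**What to change.** In the RFS definition in Protocol 9.4.3, replace morphologic relapse with *recurrence as defined in Appendix 4 (blood, marrow or extramedullary; molecular or cytogenetic reappearance alone excluded)*. Use the same defined term for relapse in the EFS definition, in the RFS censoring sentence, and in the endpoint tables of the Synopsis, Protocol 3.0 and SAP section 3.

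The cost is a few words in each place. The Relapse Assessment eCRF already documents recurrence. Against the literal 9.4.3 rule, the only analytic consequence would be that a small, unknown number of RFS events are added or dated earlier.

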9.2 Sample Size Determination

Based on a completed study of newly diagnosed AML subjects treated with ENTO, it is anticipated that 87% of *NPM1*-m subjects will achieve CR ([Walker 2020](#)). Based on analysis of a historical dataset from the Cancer and Leukemia Group B Alliance ([Mims et al, 2021](#)) showing a 68% CR rate in 107 *NPM1*-mutated/*FLT3-ITD* negative patients ≥ 60 years of age treated with 7+3 induction, a conservative estimate of 70% CR rate for placebo is assumed for sample size determination. The MRD negative rate among placebo subjects achieving CR is assumed to be 60% ([Ivey et al, 2016](#)). Alternatively, it is hypothesized that 80% of subjects with CR receiving ENTO will be MRD negative. A sample size of 90 subjects per group (total of 180 subjects) will provide $> 97\%$ power to detect a difference in the MRD negative CR rate of 28% (87% x 80% = 70% for ENTO vs 70% x 60% = 42% for placebo) with a 2-sided alpha level of 0.05 (PASS 2008: Two sample test of Proportion Module). Up to 10% over enrollment is allowable in order to account for technical or logistical barriers (eg. inadequate bone marrow aspirate or poor sample quality) related to the ascertainment of MRD status in patients who achieve CR post-Chemotherapy Cycle 2.

Assuming the two-year EFS rate for the control group is 63% (hazard rate of 0.231), a total of 124 events (70 in the placebo arm, 54 in the ENTO arm) would be sufficient to provide 80% power to detect a hazard ratio of 0.6 for EFS (PASS 2008: log rank tests (Lakatos) [Hazard Rate] module) assuming 2-sided alpha = 0.05 and a total study duration of 60 months.

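### The secondary testing hierarchy omits the CR rate, does not say whether it depends on the primary, and puts overall survival behind a remitters-only RFS test

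*Protocol*

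**What the plan says.** Protocol Section 3.0 lists EFS, RFS, OS and the CR rate as secondary efficacy endpoints; the last is given as "CR rates after 2 cycles of chemotherapy, as defined by ELN 2017 criteria". Section 9.4.3 states the purpose of the hierarchy: "To avoid inflation of Type I error for the secondary endpoints, statistical comparisons will be made at the time of the confirmatory analysis". The procedure is a "hierarchical approach with EFS tested first followed by RFS, and then overall survival", with the detail left to the SAP. The CR rate appears only in the general statement "Categorical secondary endpoints will be analyzed similarly to the primary efficacy endpoint". Section 9.4.1 sets two-sided 0.05 for any test.

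RFS is restricted to remitters: "For subjects who achieve CR, relapse free survival (RFS) is defined as the time from CR to morphologic relapse" (or death). EFS and OS run from randomisation in all subjects, and EFS counts induction treatment failure as an event at Day 1.

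Section 9.2 assumes "87% x 80% = 70% for ENTO vs 70% x 60% = 42% for placebo" for the primary. For EFS it assumes 63% at two years on placebo (hazard 0.231 per year), a hazard ratio of 0.6, and 124 events (70 placebo, 54 ENTO) for 80% power over 60 months. It gives no RFS assumption and no RFS power.

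The SAP was finalised after termination. Section 4.2 records 15 randomised subjects, and Sections 4.1 and 4.4.3 rule out formal testing and inference. The promised detail on the hierarchy was therefore never supplied.

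**The concern.** The stated aim covers the secondary endpoints, but the procedure covers three of the four efficacy ones. A CR-rate test at 0.05 beside an EFS chain at 0.05 is two chances of a false claim. The primary and the EFS chain are analysed at different times (Sections 9.5.3 and 9.5.4), each at 0.05, and the protocol is silent on whether one depends on the other.

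The order raises a separate problem. In a fixed sequence, a non-significant RFS result ends formal testing before OS. RFS compares ENTO remitters with placebo remitters, and the plan expects ENTO to bring more subjects into remission. The two groups are then not comparable by randomisation, and the RFS contrast can differ from the effect in all randomised subjects. The most important all-randomised endpoint would depend on a selected comparison for which no power is stated.

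**Working it through.** **Plan's own figures.** Control hazard: -ln(0.63)/2 = 0.231. Events for hazard ratio 0.6 at 80% power, 1:1, two-sided 0.05: 121 (Schoenfeld) and 126 (Freedman), which bracket the stated 124. Primary power at 70% vs 42% with 90 per arm: 97.1%. These reproduce.

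**Error rate.** For independent tests at 0.05 the chance of at least one false claim is 1 - 0.95² = 9.75% for two and 1 - 0.95³ = 14.3% for three. The endpoints are positively correlated, so the true figures are lower. Simulations under the global null (90 per arm, CR 70% and MRD-negative 60% of CR in both arms) gave 8.7-9.5% for CR rate or EFS, 9.4% for primary or EFS, and 12-13% for all three. Each test alone was near 5%.

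**Implied RFS.** Taking 1 minus the CR rate as the proportion with induction failure, and since those failures are Day 1 events, RFS at time t is roughly EFS(t) divided by the CR rate.

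- Two-year figures: ENTO EFS = 0.63^0.6 = 0.758. RFS = 0.63/0.70 = 0.900 on placebo and 0.758/0.87 = 0.871 on ENTO. Hazard ratio = ln(0.871)/ln(0.900) = 1.31. The sign changes at an ENTO CR rate of 0.758/0.900 = 84.2%.
- 60-month horizon: with hazards 0.231 and 0.6 × 0.231 = 0.139, EFS is 0.315 and 0.500. RFS = 0.315/0.70 = 0.450 and 0.500/0.87 = 0.575; hazard ratio 0.69. The curves cross at ln(0.87/0.70)/(0.231 - 0.139) ≈ 2.35 years.
- 70/54 event split, 90 per arm: remove induction failures, 0.30 × 90 = 27 and 0.13 × 90 = 11.7. Remaining events are 43 of 63 placebo and 42.3 of 78.3 ENTO remitters; hazard ratio = ln(1 - 0.540)/ln(1 - 0.683) ≈ 0.68. With 99 per arm it is about 0.75.

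The readings disagree because the inputs do not fit together. Exponential EFS at hazard 0.231 does not fall to 70% until -ln(0.70)/0.231 = 1.54 years, yet a 70% CR rate puts 30% of placebo subjects at Day 1 events.

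**RFS as a gate.** Log-rank simulation: 3,000 trials, 90 per arm, five years of follow-up for all, exponential times after remission.

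| Reading | RFS HR | EFS events | EFS significant | EFS and RFS both significant |
|---|---|---|---|---|
| Two-year figures | 1.31 | 76 | 25% | 0.3% |
| 70/54 split | 0.68 | 124 | 85% | 44% |
| HR 0.6 after remission, control hazard 0.231 | 0.60 | 121 | 93% | 65% |

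Given a significant EFS result, RFS therefore stops the sequence before OS in 1 - 0.443/0.853 = 48% of trials on the second reading and 1 - 0.647/0.931 = 31% on the third. A variant of the third that holds placebo EFS at 63% at two years gives 27% for both, but only 65 events.

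**The case against.** A fixed sequence controls error in any order, so placing RFS before OS is a choice and not a Type I error fault. This stands; the objection to the order concerns power and interpretation.

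The CR rate may be intended for estimation only. Section 9.4.2.2, whose method it borrows, describes a risk difference with a confidence interval, and Section 9.4.3 can be read as confining formal comparisons to the three named endpoints. This partly stands: the 9% applies only if the CR rate is tested and claimed. No sentence excludes that.

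The missing link to the primary is silence that was deferred to the SAP. This also stands. A reader might infer that the protocol permits an EFS claim after a failed primary, but it does not say so.

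A reader might also infer from the 1.31 that the plan's own numbers predict an RFS result in the wrong direction, so that OS could not be reached. The documents do not support this. The figure uses only the two-year point. The same paragraph's 60-month duration and event split imply about 0.69 and 0.68, favouring ENTO, and the two-year reading extended to five years yields 76 EFS events, not 124.

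**Conclusion.** The concern holds as a gap in the protocol's design. The testing family is not fully defined: one listed secondary endpoint has no place in the error control, and the relation to the primary is unstated. If CR rate and EFS are both tested at 0.05, the error rate is about 9%, and about 12-13% with the primary counted.

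The direction of RFS is undetermined by the planning inputs. Even on the two favourable readings that deliver close to the planned 124 events, EFS and RFS both succeed in only about 44-65% of trials. RFS is thus a weak gate that often blocks OS when ENTO works. These figures assume that induction failure equals 1 minus the CR rate, exponential times after remission, and five years of follow-up for everyone; the documents state none of these.

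Nothing reported is affected, because no testing was done. The point matters for the design record and for any reuse of this plan.

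**What to change.** In Section 9.4.3, name every secondary endpoint that may carry a formal claim and give one fixed sequence at two-sided 0.05, for example EFS, then OS, then CR rate. State whether the sequence starts only if the primary MRD-negative CR test is significant. If it does, error across primary and secondary endpoints is held at 5%; if it does not, the secondary family is held at 5% but the combined error can reach 0.05 + 0.05 = 10%. Put RFS last, or report it descriptively with a hazard ratio and 95% CI, noting that it compares remitters only. If the CR rate is for estimation only, say so.

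This is a change of wording, with no added subjects or data. RFS loses its early formal claim, and a CR rate placed after OS can be claimed only if OS succeeds. The sponsor may choose another order, provided it is fixed in advance and OS does not wait on RFS.
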